### **5.2. Exclusion Criteria**

- Subject has known esophageal deformity, or evidence of esophageal trauma, prior radiation therapy involving the esophagus, or previous esophageal disease (for example, known esophageal varices, cirrhosis, history of esophagectomy, previous swallowing disorders or dysphagia, achalasia, known ingestion of acidic or caustic poisons within the prior 24 hours etc.).
- Subject is incarcerated
- Subject is pregnant or plans to become pregnant
- Subject has a silicone allergy
- Subject has esophageal bleeding prior to EnsoETM insertion

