### **4. Study Design and Endpoints**

#### **4.1. Description of Study Design**

Single-center, randomized pilot study of esophageal temperature management using Attune Medical's EnsoETM during RF ablation vs. RF ablation without the EnsoETM.

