## 7. Study Procedures and Schedule

### 7.1. Study Procedures/Evaluations

#### 7.1.1. Study Specific Procedures

- Study specific imaging will include endoscopic evaluation of the esophagus one day before surgery at the time of the pre-op Transesophageal Echocardiography (TEE) and again 1-day post-op. This will include endoscopic esophageal intubation with visual assessment of the entire esophagus and grading of lesions. Coupled with this procedure will include endoscopic ultrasound assessment of the esophagus at the level of the left atrium with specific attention to the sub-mucosal layer that separates esophagus from the cardiac tissue. The patient will undergo moderate sedation during this procedure, which will accompany the TEE.
- The ECD will be placed by trained study staff following endotracheal intubation. Proper positioning will be verified. A temperature probe will be placed to verify the patient's core temperature. The target temperature will be set to the core temperature at the beginning of the procedure. Two minutes prior to ablation on the posterior wall the target temperature will be changed to the minimum temperature setting which will allow for maximal cooling. Cooling will take place throughout the duration of posterior wall ablation. After ablation in this territory is complete the target temperature will return to the patient's core temperature. The device will be removed at the completion of the procedure by anesthesiology when there is no further need for an orogastric tube.
- LET monitoring will not be performed in the patients of the intervention group as the ECD is prohibitive. Therefore, ice lavage of the esophagus, as detailed below, will not be performed in this group.

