#### 7.1.2. Standard Care Procedures

- Medical History will be obtained by interview and will involve identification of contraindications to the use of the ECD. This includes a history of esophageal perforation or varices. An allergy to silicone will be assessed.
- The patient's active medication list will be reviewed as is standard protocol for atrial fibrillation ablation, but this is not specific to the study as there are no medications that would impact the use of the ECD.
- All subjects will be on Protonix (40mg; twice daily) immediately following surgery for 30 days and anticoagulation for 3 months following surgery.
- The physical exam will be performed as is customary for the procedure. Study specific exam is included as part of the airway assessment which is performed on a regular basis by anesthesiology. The oropharynx will be assessed prior to placement of the ECD.

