## **7.2. Radiographic Procedures/Evaluations**

### **7.2.1. Esophagoscopy**

The patient will present for endoscopic evaluation the day prior to surgery. During this time the patient will undergo moderate sedation with continual monitoring of vital signs. Following adequate sedation the proceduralist will proceed with esophageal intubation with visual assessment of the entire esophagus and grading of lesions (Zargar classification). Furthermore, the submucosal tissue will be assessed with EUS at the level of the left atrium. This procedure will be preceded by TEE with moderate sedation maintained.

The day following the PVI the patient will undergo repeat endoscopic evaluation of the esophagus in the same manner as detailed above. The proceduralist will document their findings including the condition of the sub-mucosal esophageal tissue as noted by EUS.

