### **7.3.3. Surgical Procedure Visit (Visit 3)**

Subjects will undergo the RF ablation procedure within 30 days of randomization unless there is a medically valid reason to delay the procedure. The procedure is described below. Details of the procedure are referenced in section 7.1.2 of this study protocol. The investigator's procedure note will be included in the study files to gather endpoint and exploratory data.

The following day the patient will undergo repeat endoscopic evaluation in the same fashion as the prior study with moderate sedation. This will include visual assessment of the esophagus with video imaging as well as EUS at the area of interest near the left atrium at the level of the pulmonary veins.

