### 9.2. Measures to Minimize Bias

#### 9.2.1. Enrollment / Randomization / Masking Procedures

Patients will be randomly assigned on a 1:1 ratio (ECD during RF ablation:No ECD device during RF ablation) one of two study groups. A random permuted block will be generated to decide the randomization assignments. The rationale for the use of random permuted block assignment is to ensure a 1:1 group assignment ratio.

To minimize bias, the individual who evaluates the radiographic imaging will be blinded to the study hypotheses and subject's group assignment, so as not to influence his/her evaluation of the condition of the subjects' esophagus. It is not possible to blind the PI, as he will be performing the procedure. Further, the patient will be blinded to the study group to which he or she was assigned. Study subjects will be debriefed regarding his or her study assignment at the final study visit. The informed consent form will explain this process to subjects. The rationale for blinding subjects to their study group assignment is to minimize the influence of the Placebo Effect.

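### The esophageal-bleeding exclusion in section 5.2 is timed to EnsoETM insertion, which falls after randomisation and exists only in the device arm, so it permits a one-sided exclusion

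*Protocol*

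**What the plan says.** The criterion is the last item of Protocol section 5.2: "Subject has esophageal bleeding prior to EnsoETM insertion". It is the only item there timed to a device step.

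Four other places fix when that step occurs and who undergoes it:

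- Section 7.1.1: "The ECD will be placed by trained study staff following endotracheal intubation".
- Section 7.3.3: "Subjects will undergo the RF ablation procedure within 30 days of randomization", unless there is a valid medical reason for delay.
- Section 4.1 gives the comparison as EnsoETM temperature management "during RF ablation vs. RF ablation without the EnsoETM".
- Section 9.2.1 names the second randomised group as "No ECD device during RF ablation".

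The baseline inspection of the esophagus carries no arm restriction. Section 7.2.1 says: "The patient will present for endoscopic evaluation the day prior to surgery".

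Three further rules bear on the point. The first item of section 5.2 excludes evidence of esophageal trauma, with no device anchor. Section 5.5 removes subjects with esophageal stricture or ulceration and does not mention bleeding. Section 7.5 provides for removing the device if placement causes bleeding, and does not say that the subject is then excluded.

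**The concern.** An exclusion criterion protects a randomised comparison only if it is decided before allocation, or at least at a moment and by a procedure that are the same in both arms. This criterion remains open until a moment that comes after allocation and that control subjects never reach.

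What it screens for is also close to the primary endpoint. That endpoint is esophageal mucosal damage graded by the Zargar scheme (section 4.2.1), and hemorrhages are among the Grade 2a findings in Table 1. If bleeding subjects could leave the device arm but not the control arm, the device arm would lose subjects likely to have higher grades, for a reason unrelated to cooling. Section 9.2.1 states that the operator cannot be blinded, so a decision made at the insertion step would be made knowing the allocation.

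**Working it through.** **Order of events.** Section 7.3.3 places the ablation after randomisation. Section 7.1.1 places insertion after intubation, within that procedure. Insertion is therefore after randomisation in every case. The protocol does not say whether randomisation comes before or after the baseline endoscopy, but the conclusion about insertion is the same either way.

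**Which arm undergoes each step.**

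| Step | Device arm | Control arm |
|---|---|---|
| Endoscopy and EUS the day before ablation (7.1.1, 7.2.1, 7.3.2) | yes | yes, no restriction stated |
| Oropharynx check before placement (7.1.2) | yes | no placement to precede |
| EnsoETM insertion (7.1.1) | yes | no |
| Endoscopy and EUS the day after ablation (7.1.1, 7.3.3) | yes | yes |

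The criterion in 5.2 refers to the third row. No parallel time point is given for controls.

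**Is it confined to screening?** Section 7.3.1 does judge eligibility at Visit 1. But sections 7.3.4 and 7.3.5 list an eligibility assessment again at both follow-up visits, so the document does not limit eligibility to the time before randomisation.

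**Scale.** There is no figure in the plan to reproduce, and the protocol gives no rate of pre-insertion bleeding. The rates q below are assumptions, for scale only.

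- Subjects per arm: 6 (section 1) split 1:1 (section 9.2.1) gives 6/2 = 3. One exclusion removes 1/3 = 33% of the device arm.
- Chance of at least one device-arm exclusion, 1 − (1 − q)³:
  - q = 2%: 1 − 0.98³ = 0.059
  - q = 5%: 1 − 0.95³ = 0.143
  - q = 10%: 1 − 0.90³ = 0.271
- Expected number of exclusions, 3q: 0.06, 0.15 and 0.30.
- Apparent difference with no true device effect. Assume that every bleeder would be graded 2a or worse on day 1, that non-bleeders have lesion rate p in both arms, and that bleeders are dropped from the device arm only. The control rate is then q + (1 − q)p and the device rate is p, so the difference is q(1 − p). Section 2.2 cites lesion incidences from 3% to 60%, used here for p:
  - p = 3%: 0.05 × 0.97 = 0.049 and 0.10 × 0.97 = 0.097 for q = 5% and 10%
  - p = 60%: 0.05 × 0.40 = 0.020 and 0.10 × 0.40 = 0.040

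On average the artefact is about 2 to 10 percentage points. In any single trial of this size it would be all or nothing, because one subject is 33 points of an arm.

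**The case against.** The strongest reply is that this is an ordinary enrolment criterion. It sits under enrolment, Visit 1 examines every candidate against the criteria, and the reference to insertion can be read as an outer time limit. It does not order a check at that moment. Section 7.1.1 describes intubation, placement and verification of position, with no look for blood. The check in section 7.1.2 ("The oropharynx will be assessed prior to placement of the ECD") concerns the oropharynx, not the esophagus. A site could apply the criterion evenly at the baseline endoscopy. This stands as far as it goes: the protocol does not require unequal application. It does not prevent it either, since 5.2 makes no reference to that endoscopy.

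A reader might also infer that a bleeding control could never be excluded. The documents do not support that. The trauma item in 5.2 and the stricture or ulceration rule in 5.5 apply to any subject and would catch controls whose bleeding comes with such a finding. What remains uncovered is bleeding without one.

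Two further points stand in part. Whether an excluded randomised subject is dropped from analysis is normally left to the analysis plan, which section 9.1 defers, and nothing in the protocol says that the day-1 endoscopy would be discarded. And the likelihood of bleeding on the morning of ablation is unknown. Section 2.2 speaks only of a potential contribution of the TEE probe to injury seen after ablation, and section 4.2.2 of concern about mechanical injury from TEE and LET monitoring. Neither gives a rate of visible bleeding before ablation.

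**Conclusion.** The defect holds as a matter of wording: an exclusion criterion has a time anchor that follows randomisation and exists in one arm only. Read literally, it permits a device-arm exclusion for which controls have no counterpart, on a finding related to the primary endpoint.

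The consequence is possible, not certain. It needs bleeding to be noticed between the baseline endoscopy and insertion, the subject to be excluded on that ground, and the day-1 grade then to be lost or left out. If all of this happened once, a third of the device arm would go and the comparison could tilt toward the device. The probabilities of 6% to 27% rest wholly on assumed rates of 2% to 10%, and the average artefact of 2 to 10 points rests also on counting every bleeder as Grade 2a or worse.

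A reader might go further and conclude that sites will inspect for blood at insertion and remove bleeding-prone subjects, or that the result will favour the device. The documents support neither. They describe no such inspection, the criterion covers bleeding already present and not a tendency to bleed, and bleeding caused by placement leads under 7.5 to device removal with no stated exclusion.

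**What to change.** 1. Tie the bleeding item in section 5.2 to one assessment common to both arms, the endoscopy on the day before ablation, judged without regard to allocation and, where scheduling allows, before randomisation. Since the order of randomisation and that endoscopy is not stated, state it.
2. State that a randomised subject first found bleeding after that check stays in the assigned arm for analysis, with the day-1 endoscopy counted where performed, whether or not the device was placed. This can go in the protocol or the analysis plan.
3. Reconcile section 5.2 with section 7.5. The latter covers only bleeding with device placement, so it cannot serve as the rule for bleeding seen before placement or in a control. The clinical handling of those cases is for the sponsor to state.

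The cost is a short wording change and possibly a later randomisation. If allocation is now made well ahead of the procedure (section 7.3.3 allows up to 30 days), placing it after the baseline endoscopy would move it into the last day before ablation. Where that is not feasible, a common check judged without regard to allocation still removes the arm-specific anchor. The statistical downside is a slight dilution of the contrast if a device-arm subject does not receive the device.

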### **5.3. Recruitment Strategy**

Patients will be recruited from the Principal Investigator's clinic when the decision to perform RF ablation in order to treat the patient's condition is made. The Principal Investigator (PI) or designee will provide a brief explanation of the study by describing the study objectives. If the patient is interested in learning more about the study, the PI will initiate the informed consent process.

### **5.4. Participant Withdrawal**

#### **5.4.1. Reasons for Withdrawing**

- Subject's refusal to participate

### **5.5. Participant Removal from Study**

- Subject has esophageal stricture or ulceration

- Subject death
- Physician scheduling conflict

## **6. Study Device**

### **6.1. Acquisition**

Study device is currently undergoing evaluation on-site and supply is already available on-site, with additional available upon request via standard shipping.

### **6.2. Formulation, Appearance, Packaging, and Labeling**

Study device, the EnsoETM, is a non-sterile multi-lumen silicone tube placed in the esophagus for the purpose of cooling or warming a patient while simultaneously allowing gastric decompression and drainage. Modulation and control of the patient's temperature is achieved by connecting the EnsoETM to an external heat exchanger. Two lumens connect to the external heat exchanger, while a third central lumen provides stomach access for connection to a fluid collection device with low intermittent suction for gastric decompression. The EnsoETM is made of standard medical-grade silicone. It is a single-use, disposable, non-implantable device with an intended duration of use of 36 hours or less.

Additional details can be found in the attached Instructions for Use which are packaged along with the device as a package insert.

### **6.3. Products Storage and Stability**

Describe the study device's storage needs. Include:

- Storage requirements: Store in a dry and clean place
- Stability requirements: 5C to 32C, with no humidity requirement.
- Expiration date: 3-year shelf life

### **6.4. Preparation**

The Manual of Procedures details the preparation of the study device and is attached to this protocol as an appendix.

### **6.5. Administration**

#### **Placement of the EnsoETM**

The external heat exchanger must be in proper operating condition and must have received all the required maintenance. Failure to ensure that the heat exchanger is in proper condition may result in suboptimal performance. Ensure that no contaminants are present in the heat exchanger water.

Measure the patient for EnsoETM placement carefully before use. Insertion of an excessive length of the EnsoETM into the stomach may lead to coiling, kinking, knotting, or breakage of the EnsoETM. To measure the patient for EnsoETM placement, extend the EnsoETM from the patient's lips to the earlobe and then from the earlobe to the tip of the xiphoid process (xiphisternum). Mark the location on the EnsoETM.

Follow the Instructions for Use for the external heat exchanger for all device operations, including connections to electric wall power, patient probes, and tube set connections. Connect the EnsoETM (Figure 1) to the external heat exchanger in place of a blanket or pad, using a Cincinnati Sub-Zero connector hose (CSZ P/N 286) with the connectors as shown in Figure 1. Turn on the external heat exchanger.

Ensure that the patient has a temperature probe with a monitor in use (for example, a Foley catheter temperature probe or a rectal temperature probe). The temperature probe must be connected to the external heat exchanger, as directed in the external heat exchanger's Instructions for Use. Ensure that the temperature monitor is functioning correctly and that the temperature probe is not damaged, expired, or compromised in any other way.

Select the control mode and target patient temperature on the external heat exchanger. Ensure that water is flowing through the EnsoETM, and that no leaks are present. Failure to initiate water flow prior to insertion may hinder placement of the EnsoETM.

Lubricate the EnsoETM generously with water soluble lubricant prior to insertion. Do NOT use petroleum-based products, because these may be harmful to the respiratory tract.

Insert the EnsoETM using gentle pressure posteriorly and downwards through the mouth, past the oropharynx and into the esophagus. Gently assist the passage of the EnsoETM with light pressure until the required length of tube has been inserted.

Do not use force during insertion of the EnsoETM, because this may cause bleeding and/or damage to the oropharynx or other structures. If resistance is encountered during insertion of the EnsoETM, immediately stop the procedure.

Confirm placement of the EnsoETM by the following:

- injecting 5 to 20 mL of air (with a 50 or 60 ml syringe) through the central lumen while auscultating over the stomach for a “swoosh” or a “burp” indicating gastric placement,
- aspirating gastric contents with a syringe (using a 50 or 60 ml syringe) through the central lumen, and
- confirming the location and placement of the EnsoETM with an x-ray.

Secure the EnsoETM with a securement device or tape in accordance with hospital protocol. Ensure the EnsoETM and tube set connections are not in contact with the patient's skin. Direct contact between the EnsoETM and exposed skin may cause shivering.

For stomach decompression, connect the central lumen of the EnsoETM (Figure 1) to low-intermittent suction using standard suction tubing (not supplied) and adaptor (not supplied). Always use the lowest suction setting that will effectively decompress the stomach.

The central lumen of the EnsoETM is not intended for enteral feeding or for administration of oral medication. If the central lumen of the EnsoETM becomes blocked or clogged,

standard approaches for clearing blocked gastric tubes are recommended. For example, disconnect the EnsoETM from wall suction and use a saline flush. If the standard approaches are unsuccessful, it may be necessary to remove and then replace the EnsoETM.

Monitor patient temperature using both monitors during use. Ensure that the temperature monitors are reporting temperatures that are in agreement; if the discrepancy between the two monitors is greater than 0.5°C, discontinue treatment and investigate the cause of the discrepancy. Replace the temperature probes or secondary monitor if necessary. Ensure both temperature probes remain in place without accidental dislodgement during the entire course of patient treatment. Monitor circulating coolant temperature and ensure that it does not fall below 4°C or exceed 42°C.

## 6.6. Device Specific Considerations

- Device size: The device has outside diameter less than or equal to 13.3mm, with a wall thickness of 0.65mm±0.1mm.
- Device model: *EnsoETM Model: ECD02*
- Duration of exposure: less than 36 hours
- Frequency of exposure: Single-use

## 7. Study Procedures and Schedule

### 7.1. Study Procedures/Evaluations

#### 7.1.1. Study Specific Procedures

- Study specific imaging will include endoscopic evaluation of the esophagus one day before surgery at the time of the pre-op Transesophageal Echocardiography (TEE) and again 1-day post-op. This will include endoscopic esophageal intubation with visual assessment of the entire esophagus and grading of lesions. Coupled with this procedure will include endoscopic ultrasound assessment of the esophagus at the level of the left atrium with specific attention to the sub-mucosal layer that separates esophagus from the cardiac tissue. The patient will undergo moderate sedation during this procedure, which will accompany the TEE.
- The ECD will be placed by trained study staff following endotracheal intubation. Proper positioning will be verified. A temperature probe will be placed to verify the patient's core temperature. The target temperature will be set to the core temperature at the beginning of the procedure. Two minutes prior to ablation on the posterior wall the target temperature will be changed to the minimum temperature setting which will allow for maximal cooling. Cooling will take place throughout the duration of posterior wall ablation. After ablation in this territory is complete the target temperature will return to the patient's core temperature. The device will be removed at the completion of the procedure by anesthesiology when there is no further need for an orogastric tube.
- LET monitoring will not be performed in the patients of the intervention group as the ECD is prohibitive. Therefore, ice lavage of the esophagus, as detailed below, will not be performed in this group.

